### 17.2.11 Safety Measures

The safety measures during Days 1-7 of the study are AEs, vital signs, ECGs (primarily evaluated for changes in QTcF versus time-matched controls for both doses of lofexidine and placebo), clinical laboratory measures, physical exams, and suicidal ideation and behavior. Adverse event summaries will include tabulations overall and by seriousness, severity, and causality assessment. The data from these measures recorded during Days 1-7 will be summarized descriptively by treatment group. In addition, each lofexidine group will be compared inferentially to the placebo group using chi-square tests for categorical variables and t-tests within an analysis of variance for continuous variables; the resulting p-values will not be adjusted for multiple testing.

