Descriptive statistics will be calculated for the last double-blind and last open-phase postbaseline assessment as well as changes from baseline for each hematology, coagulation and chemistry variable. Each measurement will be classed as below, within, or above normal range, based on ranges supplied by the laboratory used. Shift tables in relation to the normal range from screening to each follow-up visit will be presented.

Descriptive statistics for urinalysis will be calculated for the last double-blind and last openphase post-baseline assessment as well as changes from baseline.

Details of microscopic urinalysis will be provided in Appendix 16.2 of the report.

Vital Signs During the Double-Blind Phase

Vital signs (blood pressure and pulse [sitting or recumbent and standing], respiration, and temperature) will be measured at screening, baseline and before each dose and 3.5 hours after each dose (with the exception of the dose taken at 11 PM, where the measurement at 3.5 hours post-dose will not be done) during the double-blind phase. Summary statistics for observed and changes from baseline will be tabulated at each follow-up for each vital sign parameter and at post-baseline double-blind endpoint for each variable.

Effective: 14-Feb-13

Page 20 of 26

In addition the number and proportion of subjects having:

- Systolic blood pressure \geq 180mmHg and an increase of \geq 20mmHg from baseline
- Systolic blood pressure ≤ 90mmHg and a decrease ≥ 20mmHg from baseline
- Diastolic blood pressure ≥ 105mmHg and an increase ≥ 15mmHg from baseline
- Diastolic blood pressure ≤ 50mmHg and a decrease ≥ 15mmHg from baseline

will be summarized at each follow-up visits.

Vital Signs During the Open-Label Phase

Vital signs (blood pressure and pulse [sitting or recumbent and standing]) will be assessed for one dose every day at pre-dose and 3.5 hours post-dose on Days 8-13, with vital signs measured once pre-dose on Day 14. Summary statistics for observed and changes from baseline will be tabulated at each follow-up and at post-baseline open-phase endpoint for each variable.

Mean profiles by treatment will be presented for sitting and standing blood pressure and heart rate.

ECG

ECG data collected during the double-blind and open-label phase will be analyzed separately in a stand-alone report.

In addition, PI overall interpretation of the ECG (Normal, Abnormal NCS, and Abnormal CS) will be listed in Appendix 16.2.

C-SSRS

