6.14 Change to Planned Protocol Analysis

The following changes have been made to the planned protocol analyses sections:

Section 17.2.7 Control of the False Positive Rate and Statistical Testing Strategy

Change: All statistical tests will be two-sided at the 0.05 significance level. This is a change from the protocol, where it was specified that statistical tests would be one-sided at the 0.025 significance level.

Reason: Two-sided statistical tests at the 0.05 significance level is statistical convention for hypothesis testing.

Section 17.2.8.1 SOWS-Gossop AUC (1-7)

Change: A number of sensitivity analyses have been added and are detailed in section 16.9.2 of the statistical analysis plan.

Reason: To provide additional sensitivity analyses of log_e (SOWS-Gossop score +1) from day 1 to day 7 under differing mechanisms for missing data, including Missing at Random (MAR) and Missing Not at Random (MNAR)

Section 17.2.8.2 Completion Status

Change: A logistic regression model including fixed effects for treatment group, gender and site will be used instead of a Cochran-Mantel Haenszel test to test for a difference in completion status between the 2 Lofexidine groups and placebo.

Reason: To additionally adjust for site in the analysis and to provide an interpretation of the effect of treatment using odds ratios.

Sections: 17.2.8.3 SOWS-Gossop on Days 1, 2, 3, 5, 6 and 7 and 17.2.8.4 OOWS-Handelsman, MCGI (Subject and Rater), VAS-E, and COWS

Change: A MMRM model will be used to test for a difference in the log_e (SOWS-Gossop score +1) at each of days 1 through 7 between the 2 Lofexidine groups and placebo. This replaces planned pattern-mixture approach used in the principal analysis.

Reason: MMRM model is a standard approach for the analysis of treatment differences at different time points when there are repeated measures.

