Vital signs (blood pressure and pulse [sitting or recumbent and standing], respiration, and temperature) will be measured at screening, baseline and before each dose and 3.5 hours after each dose (with the exception of the dose taken at 11 PM, where the measurement at 3.5 hours post-dose will not be done) during the double-blind phase. Summary statistics for observed and changes from screening will be tabulated at each follow-up for each vital sign parameter and at post-baseline double-blind endpoint for each variable.

In addition the number and proportion of subjects having:

- \neq Systolic blood pressure \geq 180mmHg and an increase of \geq 20mmHg from baseline
- \neq Systolic blood pressure \leq 90mmHg and a decrease \geq 20mmHg from baseline
- \neq Diastolic blood pressure \geq 105mmHg and an increase \geq 15mmHg from baseline
- \neq Diastolic blood pressure \leq 50mmHg and a decrease \geq 15mmHg from baseline

will be summarized at each follow-up visits.

The text in bold was added to the following:

Effective: 24-Dec-2014

Page 14 of 29

Vital signs (blood pressure and pulse [sitting or recumbent and standing], respiration, and temperature) will be measured at screening, baseline and before each dose and 3.5 hours after each dose (with the exception of the dose taken at 11 PM, where the measurement at 3.5 hours post-dose will not be done) during the double-blind phase. Summary statistics for observed and changes from **screening** will be tabulated at each follow-up for each vital sign parameter and at post-baseline double-blind endpoint for each variable.

In addition the number and proportion of subjects having:

- ≠ Systolic blood pressure \ge 180 mmHg and an increase of \ge 20 mmHg from screening
- ≠ Systolic blood pressure \leq 90 mmHg and a decrease \geq 20 mmHg from screening
- \neq Diastolic blood pressure \geq 105 mmHg and an increase \geq 15 mmHg from screening
- \neq Diastolic blood pressure \leq 50 mmHg and a decrease \geq 15 mmHg from screening

will be summarized at each follow-up visits.

REFERENCES

Little, RJA and DB Rubin. Statistical analysis with missing data. Version 2. John Wiley & Sons; New York: 2002

Effective: 24-Dec-2014

Page 15 of 29

Protocol Number USWM-LX1-3003-1 Statistical Analysis Plan Addendum 1 Version: Final Issue Date: 24-Dec-2014

Effective: 24-Dec-2014

Page 16 of 29

Protocol Number USWM-LX1-3003-1 Statistical Analysis Plan Addendum 1 Version: Final Issue Date: 24-Dec-2014

Effective: 24-Dec-2014

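### SAP 6.13 omits, without declaring it, the comparison of double-blind vital signs and laboratory measures with placebo that Protocol 17.2.11 requires

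*SAP*

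**What the plan says.** **Protocol 17.2.11** sets the scope: "The safety measures during Days 1-7 of the study are AEs, vital signs, ECGs", followed by laboratory measures, physical examinations and suicidality. After asking for summaries by treatment group, it adds that "each lofexidine group will be compared inferentially to the placebo group using chi-square tests for categorical variables and t-tests within an analysis of variance" (the latter where the variable is continuous). On multiplicity it says that "the resulting p-values will not be adjusted for multiple testing".

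**SAP 6.13, vital signs in the double-blind phase**, plans description: "Summary statistics for observed and changes from baseline will be tabulated at each follow-up for each vital sign parameter", plus counts of subjects meeting four blood-pressure criteria. Addendum 1, Change 15, replaces baseline with screening as the reference: "Summary statistics for observed and changes from screening will be tabulated at each follow-up for each vital sign parameter". It alters nothing else of substance.

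**SAP 6.13, laboratory data**: "Descriptive statistics will be calculated for the last double-blind and last open-phase postbaseline assessment as well as changes from baseline". For categories, "Shift tables in relation to the normal range from screening to each follow-up visit will be presented".

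**SAP 6.14** opens with "The following changes have been made to the planned protocol analyses sections" and then goes through Protocol 17.2.7, 17.2.8.1, 17.2.8.2, 17.2.8.3 with 17.2.8.4, and 17.2.8.5, with a reason for each. Section 17.2.11 is not among them.

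**The concern.** Protocol 12.1 describes lofexidine as an alpha2-adrenergic agonist that lowers blood pressure. Blood pressure and heart rate drive the dose-hold and discontinuation rules (13.2.2, 13.2.3, 14.5.2), and vital signs are measured seven times a day on Days 1-7. How far each dose moves blood pressure and pulse relative to placebo is therefore one of the main safety questions. The change in any single arm is the drug effect plus whatever happens to all subjects over the same days of withdrawal. The randomised difference separates the two, and the protocol asked for it.

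There is also a matter of prespecification. The protocol requires tests that the SAP does not plan, and the SAP does not withdraw them. Whether to run them, and for which measures and times, is left open until the data are unblinded.

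**Working it through.** No power, precision or alpha is stated for the safety comparisons, so there is no figure to reproduce. The check is a comparison of texts, followed by arithmetic for scale.

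**1. Requirement against plan, by measure (Days 1-7)**

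| Measure in Protocol 17.2.11 | Comparison with placebo in SAP 6.13 |
|---|---|
| Adverse events | Yes: chi-squared test, each dose against placebo |
| Suicidal ideation and behaviour | Yes: Fisher's exact test on seven C-SSRS items |
| Vital signs | None: by-arm summaries and blood-pressure threshold counts |
| Laboratory measures | None: by-arm summaries and shift tables |
| ECG | Sent to a separate report, so not assessed here |

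Two measures keep a test against placebo, so the SAP did not choose to describe safety only.

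**2. Could another clause supply the comparison?**
- SAP 6.1 asks for 95% intervals on treatment comparisons. It governs comparisons that are made and creates none.
- SAP 6.1 also permits further tests if the data warrant them. A data-driven option does not replace an analysis fixed in the protocol.
- SAP 6.5 lays tables out by arm with a placebo column. That is layout, not a contrast.
- Protocol 7 speaks of a descriptive safety comparison, but between 2.4 mg and 3.2 mg, not between drug and placebo.
- Addendum 1 and Addendum 2 add no such comparison and do not mention removing one.

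**3. A related gap.** Protocol 15.5.2 gives criteria for systolic pressure, diastolic pressure and pulse. The SAP threshold list, in 6.13 and again in Change 15, has the blood-pressure criteria only. Pulse therefore gets change summaries and no threshold counts.

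**4. Precision of the omitted comparison.** Arm sizes are 225 per dose and 150 on placebo (Protocol 10.2). The documents give no SD for vital signs; 10 to 15 mmHg is an assumption.
- All subjects observed: SE = SD x sqrt(1/225 + 1/150) = 0.1054 SD. Half-width = 1.96 x 0.1054 SD = 0.207 SD, which is 2.07 mmHg at SD 10 and 3.10 mmHg at SD 15.
- Half of each arm observed (assumed): SE = SD x sqrt(1/112.5 + 1/75) = 0.1491 SD. Half-width = 0.292 SD, which is 2.92 mmHg at SD 10 and 4.38 mmHg at SD 15.

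**5. How many comparisons a remedy implies.** Seven readings a day for seven days is 49, or 48 after the first dose. With six parameters (systolic, diastolic and pulse, resting and standing) and two doses, testing every time gives 48 x 6 x 2 = 576 contrasts, of which about 0.05 x 576 = 29 would be nominally significant with no drug effect. One post-dose time per day plus the double-blind endpoint gives 8 x 6 x 2 = 96, or about 5 by chance.

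**The case against.** The strongest reply is that little information is lost. Tables are by arm and, under SAP 5.1, give n, mean and SD, so a difference and its interval can be computed from them. Observed values, threshold proportions and shift tables are also shown by arm. This stands. A reader might infer that the vital-sign effect is never estimated against the randomised control. The documents support only that no between-arm difference, interval or test is planned in the SAP text. The separate ECG report (which would include ventricular rate) and the table layouts are not in the public text and cannot be checked.

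A second reply is that the signal is partly captured elsewhere. Protocol 15.5.2 has vital signs meeting its criteria recorded as adverse events, and treatment-emergent events are tested against placebo. This also stands in part, but it is unclear whether that test is run per preferred term, and event counts do not give the mean effect in mmHg or beats per minute.

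A reader might blame Change 15, or think that a screening reference distorts the result. Neither holds. The omission is already in the main SAP, screening is the reference in the protocol's own criteria (13.2.2, 13.2.3, 15.5.2), and a common reference cancels in the difference between arms. Nor should one calculate how often a single-arm change would look significant, because no within-arm test is planned.

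Finally, observed-case contrasts on later days are not cleanly randomised, because the dose-hold and discontinuation rules act on low blood pressure and pulse. This is a real limit on interpretation, and it applies equally to the by-arm summaries.

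**Conclusion.** The point holds as a conflict between the two documents that should be reconciled. Protocol 17.2.11 requires a comparison with placebo for vital signs and laboratory measures; SAP 6.13 and both addenda do not plan one; SAP 6.14 does not declare the change. The protocol's pulse criteria are also missing from the threshold counts.

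The weight is moderate. These are unadjusted safety comparisons that support no confirmatory claim, and the efficacy analysis is unaffected. The comparison would nevertheless be informative: about 2.1 to 3.1 mmHg either side of the estimate with full retention, and 2.9 to 4.4 mmHg with half. Those ranges rest on the assumed SD of 10 to 15 mmHg and the planned arm sizes. The textual finding rests on neither.

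**What to change.** Amend SAP 6.13 for the double-blind phase, for each dose against placebo:

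- **Vital signs.** Give the difference in mean change from screening with 95% CI, for resting and standing systolic pressure, diastolic pressure and pulse, using ANOVA or ANCOVA on the screening value. Restrict this to a small prespecified set, for example the double-blind endpoint the SAP already names (stating which reading that is) and one post-dose time per day. Protocol 17.2.11 does not ask for tests at every time point.
- **Laboratory measures.** Give the difference in mean change from baseline with 95% CI at the last double-blind assessment.
- **Threshold counts.** Give the risk difference with 95% CI and the protocol's chi-square test, and add the pulse criteria from Protocol 15.5.2 to the list.
- **Labelling.** Mark p-values as unadjusted, and note that later-day contrasts include only subjects still on treatment.

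If any part of 17.2.11 is being dropped on purpose, record it in 6.14 with the reason.

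The cost is SAP wording and extra table columns from data already collected. The downside is more unadjusted safety comparisons (up to 96 for vital-sign means in the example, and two per laboratory analyte), which the protocol already accepts. Fewer summary times would reduce the number further.

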## 7 STUDY OBJECTIVES

The primary objective of this study is to investigate the efficacy, safety, and dose-response of lofexidine (2.4 mg or 3.2 mg per day) in reducing withdrawal signs and symptoms and facilitating completion of detoxification/extending treatment retention in subjects undergoing detoxification from short-acting opioids in a double-blind inpatient setting (Days 1-7) followed by an open-label inpatient/outpatient setting (Days 8-14).

It is hypothesized that a daily dose of either 2.4 mg or 3.2 mg lofexidine will achieve greater efficacy than placebo with respect to overall symptom relief over the first 7 days of opioid withdrawal (primary endpoint) and will increase the likelihood of subjects completing Days 1-7 of treatment (secondary endpoint). Further, safety measures in the 2.4 mg and 3.2 mg total daily dose groups will be compared descriptively to assess whether the lower dose results in fewer and less severe adverse events than does the higher dose.

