### 15.5.2 Vital Signs

Vital signs (systolic and diastolic blood pressure, pulse, respiration, temperature) are to be measured at screening for all subjects.

During Days 1-7, resting (sitting or recumbent, if required, for treatment of an adverse event) and standing systolic and diastolic blood pressure and pulse; respiration, and temperature will be measured at Baseline and on Days 1-7, within 30 minutes before receipt of study medication at 8 AM, 1 PM, 6 PM, and 11 PM and 3.5 hours ( $\pm 15$  minutes) after receipt of study medication at 8 AM, 1 PM, and 6 PM.

During open-label treatment, in an inpatient or outpatient setting, vital signs including resting (sitting or recumbent, if required, for treatment of an adverse event) and standing systolic and diastolic blood pressure and pulse will be measured at least once daily before dosing and 3.5 hours ( $\pm 30$  minutes) after dosing on Days 8-13 and once before a dose on Day 14. If subjects are being treated on an outpatient basis and cannot stay in the clinic for measurement of the 3.5-hour post-dose vital signs required on Days 8-13, they will be given a portable digital blood pressure machine for measurement of their vital signs at this required time point. They will also be provided a diary ([Appendix 8](#)) to record the measurements.

For the orthostatic blood pressure readings, subjects will remain at rest for 3 minutes before a blood pressure reading, and then stand for 3 minutes before a second blood pressure reading is taken. If a subject demonstrates potentially clinically significant vital signs, as per any one of the criteria (i.e., systolic values, diastolic values, or pulse values meet the specified criteria) in the guidelines shown below, the event should be recorded in the subject's source document and eCRF as an AE or SAE (see [Sections 15.5.1, 16.7, and 16.8](#)) and the subject should be followed until medically stabilized to the satisfaction of the attending physician. Additional dose-hold and discontinuation criteria are provided in [Sections 13.2.2 and 13.2.3](#), respectively.

Vital Sign Parameter	Observed Value	A N D	Change Relative to Screen	
Systolic Blood Pressure	$\geq 180$ mmHg		A N D	Increase of $\geq 20$ mmHg
	$\leq 90$ mmHg			Decrease of $\geq 20$ mmHg
Diastolic Blood Pressure	$\geq 105$ mmHg			A N D
	$\leq 50$ mmHg	Decrease of $\geq 15$ mmHg		
Pulse	$\geq 120$ bpm	A N D	Increase of $\geq 15$ bpm	
	$\leq 50$ bpm		Decrease of $\geq 15$ bpm	

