5.2 Categorical

Unordered categorical and ordered categorical (depending on the number of categories) variables will be presented in contingency tables with cell frequencies and percentages for the number of non-missing observations and frequencies for the number of missing observations apart from disposition of subjects, concomitant medications, measurement of treatment compliance and adverse events where percentages will be presented for the population.

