6. ANALYSIS PLAN

6.1 General

The treatment groups will be labelled as 2.4 mg Lofexidine, 3.2 mg Lofexidine and Placebo within the statistical output. In addition the 2.4 mg Lofexidine and 3.2 mg Lofexidine doses are

Effective: 14-Feb-13

Page 5 of 26

combined to form a single Lofexidine treatment group for presentation of safety data. Subject data in Appendix 16.2 listings will be ordered by treatment group, site and subject.

All statistical tests for efficacy will be 2-sided at the α =0.05 significance level.

All comparisons between the treatments will be reported with 95% confidence intervals for the difference. P-values will be rounded to four decimal places.

Only scheduled post-baseline laboratory and vital signs values will be tabulated. Post-baseline repeat/unscheduled assessments will be disregarded, although they will be listed in the relevant appendices to the report; in particular all clinically significant values will be noted.

All calculations and figures will be produced using SAS Version 9.3³ or higher.

All summaries and analyses documented below will be presented in the final integrated statistical/clinical report and tables that will be based on the E3 guidelines published by ICH. However, it is noted here that no analysis plan prepared in advance of the data can be absolutely definitive and so the final report may contain additional tables or statistical tests if warranted by the data obtained. The justification for any such additional analyses will be fully documented in the final report.

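### The SAP's double-blind vital-sign outlier table leaves out the protocol's two pulse criteria and counts subjects only visit by visit, so as written it gives no ever-met rate per arm

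*SAP*

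**What the plan says.** Protocol 15.5.2 sets paired criteria, an observed value together with a change from screening, each with a high and a low side. They apply to three parameters ("i.e., systolic values, diastolic values, or pulse values meet the specified criteria"). That makes six criteria, and a crossing of any one should be recorded as an adverse event.

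SAP 6.13 carries the four blood-pressure pairs into a table introduced with "In addition the number and proportion of subjects having", which "will be summarized at each follow-up visits". Addendum 1 Change 15 reopened this list and changed the reference from baseline to screening. It kept the same four criteria and the same per-visit count. Addendum 2 does not touch the section. The separate double-blind endpoint summary in 6.13 concerns observed values and changes, not these counts.

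Three other places bear on the point:

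- Protocol 17.2.11 names vital signs as a safety measure and says that "each lofexidine group will be compared inferentially to the placebo group using chi-square tests for categorical variables".
- SAP 6.1 keeps repeat and unscheduled readings out of the tables, "although they will be listed in the relevant appendices to the report; in particular all clinically significant values will be noted".
- SAP 5.2 bases categorical percentages on non-missing observations, "apart from disposition of subjects, concomitant medications, measurement of treatment compliance and adverse events where percentages will be presented for the population".

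**The concern.** Two things a safety reader would want are not in the written table.

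The first is pulse. Low heart rate is a dose-hold criterion (protocol 13.2.2) and a discontinuation criterion (13.2.3), and symptomatic bradycardia with certain features is a cardiovascular discontinuation event (14.5.2). Yet pulse is the one parameter of 15.5.2 with no threshold count, and no reason is given.

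The second is the unit of counting. A row per visit shows how many subjects were beyond a cut-off at that visit. It does not show whether the same few subjects recur or whether different subjects appear each time. Two arms can have identical rows and different numbers of subjects ever affected. Under SAP 5.2 the visit percentages also rest on subjects with a value at that visit, so a subject who has left the study drops out of later denominators.

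**Working it through.** The documents state no figure for this table, so there is none to reproduce. The check is an item-by-item comparison, a count of readings, and a bound.

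**1. Criteria carried over.** Protocol 15.5.2 has systolic high and low, diastolic high and low, and pulse high and low: 6. SAP 6.13 with Change 15 has systolic high and low and diastolic high and low: 4. Missing: pulse high and pulse low.

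**2. Scheduled readings in Days 1-7.** Protocol Table 1, footnote (i), gives one reading before each of 4 doses and one 3.5 hours after 3 of them.

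- Total: (4 + 3) × 7 = 49.
- Less the Day 1 reading before the first dose, which is not follow-up: 49 − 1 = 48.
- Of these, 3 × 7 = 21 are 3.5-hour readings and 4 × 7 − 1 = 27 are pre-dose readings.

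**3. What visit counts can say about ever-met counts.** With k subjects beyond a cut-off at each of V visits, the number ever affected is at least k (the same subjects each time) and at most k × V (no overlap). The SAP does not say whether a visit is a study day (V = 7) or a scheduled time point (V = 48). With the planned 225 subjects per lofexidine arm, no dropout, and assumed values of k:

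| k per visit | V | Fewest ever affected | Most ever affected |
|---|---|---|---|
| 1 | 7 | 1/225 = 0.4% | 7/225 = 3.1% |
| 2 | 7 | 2/225 = 0.9% | 14/225 = 6.2% |
| 5 | 7 | 5/225 = 2.2% | 35/225 = 15.6% |
| 2 | 48 | 2/225 = 0.9% | 96/225 = 42.7% |

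The last row is an arithmetic limit, not an expectation. For two doses with identical daily rows of 2, the ever-met rates could differ by at most (14 − 2)/225 = 5.3 percentage points. That takes full overlap in one arm and none in the other.

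**4. Does the pulse criterion relate to the stopping rule?** Exclusion criterion 6 requires a heart rate of at least 55 bpm. A later reading below 40 bpm is then a fall of more than 55 − 40 = 15 bpm and is below 50 bpm, so it also meets the low-pulse criterion of 15.5.2. The dose-hold rule (below 50 bpm and more than 20% below screening) is not nested in this way. From 60 bpm to 47 bpm is a fall of 13/60 = 21.7%, but only 13 bpm.

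**5. Which test fits an any-time row.** Against 150 on placebo with no cases, 2 cases among 225 give an expected placebo count of 2 × 150/375 = 0.8, too small for chi-square. Fourteen cases give 14 × 150/375 = 5.6, which is adequate.

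**The case against.** The best answer is that the information is largely covered elsewhere. Crossings of all six criteria, pulse included, should be recorded as adverse events, and SAP 6.13 tabulates treatment-emergent events per subject by preferred term, severity and relationship, with a chi-square test on the share with at least one. Pulse also appears in the summary statistics with minimum and maximum, in mean heart-rate profiles, and in listings. Much of this stands. It does not yield the missing number: preferred-term counts also include blood-pressure and pulse symptoms recorded without a crossing (15.5.2), extremes do not count subjects, and listings are not rates by arm.

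Four stronger readings are tempting, and the documents do not support them.

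- A reader might infer a breach of the protocol. Section 15.5.2 uses the criteria to trigger adverse-event recording and prescribes no outlier table.
- A reader might infer that the stated dose comparison fails. Protocol section 7 says safety measures will be "compared descriptively to assess whether the lower dose results in fewer and less severe adverse events than does the higher dose". That sentence speaks of adverse events, and those are tabulated per subject.
- A reader might infer that the 17.2.11 tests were dropped for vital signs, because the visible SAP names none. SAP 6.14 opens with "The following changes have been made to the planned protocol analyses sections" and does not list 17.2.11. That silence is equally consistent with the protocol plan still standing.
- A reader might infer that the final report cannot contain an any-time row. The table shells are not visible, SAP 6.1 allows further tables, and the count can be derived from data already collected.

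**Conclusion.** The point holds as a low-severity improvement. The written SAP tabulates four of the six criteria of protocol 15.5.2, gives no threshold count for pulse, and specifies no share of subjects per arm who ever met a criterion. Per-visit counts do not determine that share. The 0.9% to 6.2% range for a row of 2 of 225 per day shows how wide the gap can be. It rests wholly on assumed rates, planned arm sizes, no dropout and one visit per day, and it is not a prediction of what this trial will show. The conclusion is about the SAP text only.

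**What to change.** In SAP 6.13:

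- Add the two pulse criteria of protocol 15.5.2, relative to screening.
- For all six criteria, add a row for any time during Days 1-7, by arm. Count every scheduled reading after the first dose, both pre-dose and 3.5-hour (48 per subject if complete). Restricting it to 3.5-hour readings would discard 27 of the 48, including the pre-dose readings on which dose-holds are judged.
- Show resting and standing readings separately.
- Use the Safety population as the denominator, and say so, since SAP 5.2 would otherwise default to non-missing observations.
- State whether repeat or unscheduled readings count; SAP 6.1 now excludes them from tables.
- Show 3.2 mg against 2.4 mg descriptively. The any-time row is the natural variable for the chi-square comparison with placebo already planned in protocol 17.2.11, with Fisher's exact test where expected counts are small.

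The cost is a few more table rows from data already collected and a few unadjusted safety p-values. No new assessments are needed.
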